### 9.3. Outcome 3: Secondary Outcome Measure

- 9.3.1. **Title 3:** The effect of DHA and EPA Omega-3 PUFA fish oil supplementation on brain imaging markers of sub-concussion injury collegiate football athletes over the course of the American football season.
- 9.3.2. **Time Frame 3:** 25 weeks from baseline to end of treatment
- 9.3.3. **Description 3:** (not required) MRI scans were obtained at baseline and end of treatment.

#### 9.4. Outcome 4: Secondary Outcome Measure

- 9.4.1. **Title 4:** The effect of genotype differences on DHA and EPA treatment outcomes on blood based biomarker or brain MRI imaging biomarker as described in specific aim 1.
- 9.4.2. **Time Frame 4:** 32 weeks from baseline to one month post treatment and post end of football season.
- 9.4.3. **Description 4:** (not required)

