4.7. Data Monitoring Committee: Yes4.8. FDA Regulated Intervention: No

### 5. Study Description

5.1. **Brief Summary:** A short description of the clinical study, including a brief statement of the clinical study's hypothesis, written in language intended for the lay public. Limit: 5000 characters.

American football is one of the most popular sports in the U.S. Yet this sport is associated with increased risk of concussion (also known as mild traumatic brain injury, or mTBI) and subconcussive injury from repeated head impacts (RHI) due to the aggressive and highspeed nature of the game. Current protective equipment used by players are not sufficient to reduce concussion incidence and severity, nor are there any therapeutics available to prevent concussion. This study is a randomized, double-blind, placebo controlled trial, including 38 research participants, to determine whether an omega-3 polyunsaturated fatty acids (PUFA) fish oil supplement containing 3.0 grams of docosahexaenoic acid (DHA; 22:6n-3) and eicosapentaenoic acid (EPA; 20:5n-3) can reduce blood biomarkers of sub-concussion injuries compared to placebo (high-oleic safflower oil) over a course of the American football season among collegiate football athletes. Secondary outcomes include 1) determining the effect of daily DHA and EPA supplementation on brain imaging markers of sub-concussion injuries, and 2) a responder analysis to determine whether genotype differences in fatty acid desaturase 1 (FADS1), FADS2, elongation of very long chain fatty acids 2 (ELOVL2), and ELOVL5 genes affect treatment outcome of DHA. An exploratory outcome is the discovery of novel and more sensitive metabolic or lipidomic biomarkers of sub-concussion injury. The dosage of DHA/EPA used in this study is generally safe, and procedures involved, monthly blood draws, surveys, and Magnetic Resonance Imaging (MRI), pose minimal risks to participants. While this study provides no direct benefit to participants, successful outcomes of this study can benefit the society by shedding light on development of potential preventative therapeutics for sports-induced mTBI and brain injury from RHI. The risk-benefit profile is appropriate for conducting this study. Based on preclinical studies and previous clinical study results, we expect that in comparison to placebo treatment, DHA and EPA treatment throughout the course of one American football season can maintain lower levels of sub-concussion associated biomarkers,

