  - 8.6.3. **Intervention 2 Description:** Participants consumed a placebo consisting of encapsulated high-oleic safflower oil. Each placebo capsule contains 866.9 mg/capsule active ingredient. The placebo intervention included consumption of 6 capsules 5 days a week for 25 weeks. A certificate of analysis confirming manufacture date (06/03/2019), active ingredient (safflower oil), fill weight (866.9 milligrams), and microbiology safety (all negative), and disintegration time (3 minutes) was provided.
- 8.7. **Arm/Intervention Cross-Reference:** Arm 1 = Intervention 1; Arm 2 = Intervention 2
- 9. Outcome Measures
  - 9.1. Outcome 1: Primary Outcome Measure
    - 9.1.1. **Title 1:** The effect of DHA and EPA Omega-3 PUFA fish oil supplementation on blood biomarkers of brain injury compared to placebo (high-oleic safflower oil) over a course of

Study Title: Study of Effect of Docosahexaenoic Acid (DHA) and Eicosapentaenoic acid (EPA) on Biomarkers of Sub-concussion Injuries in American Football.

IRB #: 1904553365

the American football season among collegiate football athletes exposed to repeated subconcussive head impacts.

- 9.1.2. **Time Frame 1:** 32 weeks from baseline to one month postseason/treatment
- 9.1.3. **Description 1:** (not required) Blood-based biomarkers for sub-concussion injury (neurofilament light (NFL), Tau protein (Tau), ubiquinone C-terminal hydrolase L1 (UCH-L1)) and can lower inflammatory cytokines (C-reactive protein (CRP), tumor necrosis factor 1 (TNF-α), interleukin 6 (IL6)) will be measured at baseline, mid-treatment, post treatment, and one month (recovery) after the end of treatment and the football season.

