#### Continuous outcome measures include:

- Biomarkers NFL
- Cardiometabolic markers TNF-a, IL-6
- Lipid panel TG, HDL-C, LDL-C
- GC-FID for both RBC and Plasma results in 23 free fatty acids concentrations

For these continuous outcomes, we will use a longitudinal mixed-effects model framework to look at both individual and group-level changes from baseline over time. Outcome measures will be transformed where appropriate (e.g., log, sqrt, Box-Cox). Covariates will include age, position, genotypes, treatment, and starter/non-starter, as well as a treatment x starter/non-starter interaction. We will also graphically explore the trajectories of the different biomarkers over time.

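### Secondary Outcome 4 asks whether genotype changes the supplement effect, but the SAP enters genotypes only as covariates and names no genotype-by-treatment term, so the listed model cannot answer it

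*Protocol*

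**What the plan says.** Protocol section 9.4 defines Secondary Outcome 4 as "The effect of genotype differences on DHA and EPA treatment outcomes on blood based biomarker or brain MRI imaging biomarker", with the marker set given only by the words "as described in specific aim 1". The Brief Summary (Protocol 5.1) describes the same objective as "a responder analysis to determine whether genotype differences in fatty acid desaturase 1 (FADS1), FADS2", together with ELOVL2, and asks whether these and "ELOVL5 genes affect treatment outcome of DHA".

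The SAP refers to genotype in one place, the model for the continuous outcomes: "Covariates will include age, position, genotypes, treatment, and starter/non-starter, as well as a treatment x starter/non-starter interaction". The outcomes listed for that model are NFL, "Cardiometabolic markers TNF-a, IL-6", the lipid panel and the fatty acids. No imaging marker is listed, although Protocol 9.3.3 records that "MRI scans were obtained at baseline and end of treatment".

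The SAP gives no genotype-by-treatment term, no genotype-stratified analysis, no definition of a responder and no genotype coding.

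**The concern.** Outcome 4 is a question of effect modification: is the difference between supplement and placebo larger in some genotypes than in others? A genotype covariate answers a different question, namely whether marker levels differ by genotype in both arms alike. The SAP writes out an interaction where it wants effect modification by starter status and writes none for genotype.

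At stake is a named secondary outcome. The trial is recorded as completed (Protocol 2.2). If the genotype analysis is first defined once results are in view, four genes and several markers leave many possible comparisons, each estimated from 38 players. A reader could not tell which had been intended.

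**Working it through.** **1. The plan's own power figures.** Inputs from the SAP power section: α = 0.05, d = 0.6 with 44 per group, d = 0.86 with 22 per group. Power ≈ Φ(d·√(n/2) − 1.96), two-sided.
- 44 per group: 0.6 × √22 = 2.814, and Φ(0.854) = 80.4% (79.5% by the t-test).
- 22 per group: 0.86 × √11 = 2.852, and Φ(0.892) = 81.4% (79.6% by the t-test).

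Both reproduce the stated 80%. They concern comparisons of two groups. The SAP gives no figure for a genotype interaction.

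**2. What the listed model can estimate.** Let T be treatment, S starter status and G genotype. The relevant terms are

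E(Y) = … + β_T·T + β_S·S + β_TS·T·S + β_G·G.

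The supplement-minus-placebo difference is β_T + β_TS·S. It depends on S but not on G, because β_G·G is the same in both arms and cancels. Adding a term θ·T·G changes the difference to β_T + β_TS·S + θ·G, and θ is the quantity Outcome 4 asks about.

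Numerical check with one time point and 40,000 simulated players, half in each genotype, and true supplement effects of 0 and −0.8. The average is 0.5 × 0 + 0.5 × (−0.8) = −0.40. The listed model returned a treatment coefficient of −0.38, with a treatment-by-starter term near zero and no genotype contrast. With treatment by genotype added, the difference between genotypes was estimated as −0.81.

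**3. Precision once the term is added.** Inputs: N = 38 (Protocol 7.10) or 88 (SAP, 44 + 44); 1:1 allocation (Protocol 7.4). Assumed, because the documents give no value: two genotype groups (carrier coding), carrier share f, and unit SD of the analysed change. The interaction is a difference between two treatment effects, so

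SE = √[4/(N·f) + 4/(N·(1 − f))], with N − 4 degrees of freedom.

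- N = 38, f = 0.5: SE = √(0.2105 + 0.2105) = 0.649. Half-width = 2.032 × 0.649 = 1.32. Detectable with 80% power (noncentral t) = 1.87.
- N = 38, f = 0.2: SE = √(0.5263 + 0.1316) = 0.811. Detectable = 2.34.
- N = 88, f = 0.5: SE = √(0.0909 + 0.0909) = 0.426. Detectable = 1.21.

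**4. Conversion to per-visit SDs.** Suppose the contrast is the mean of the three post-baseline visits in Protocol 9.1.3 minus baseline, and any two visits correlate at 0.5 (assumed). In per-visit units:
- variance of the three-visit mean = (1 + 2 × 0.5)/3 = 0.667;
- variance of the contrast = 0.667 + 1 − 2 × 0.5 = 0.667, so its SD = 0.816.

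Then 1.32 × 0.816 = 1.08 and 1.87 × 0.816 = 1.53 per-visit SDs.

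**The case against.** **The covariate list is open and many analyses are called exploratory.** True: the list says what covariates will include, and the SAP's Data analysis section allows for exploratory work. A genotype interaction could therefore be added. But that section does not mention genotype, and an analysis that could be added is not one that is specified. The SAP also names no visit terms, so the genotype gap is part of a wider lack of detail. Adding a treatment-by-visit term alone would not close it, because the supplement effect would still not depend on genotype.

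**An interaction term is not the only route.** This stands. Genotype-stratified effects would also serve, and a responder analysis could mean a comparison within the treated arm. None of these is in the SAP either.

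**Stronger readings that a reader might infer, and that the documents do not support:**
- *The model gives one supplement effect for everyone.* It does not. The treatment-by-starter interaction allows a different effect in starters and non-starters, and only variation by genotype is excluded. After a log transform, which the SAP permits, the same effect means the same ratio.
- *No genotype analysis was ever planned.* Section 9.4 points to a specific aim 1 that is not among the documents supplied, and the Protocol is a registration-form summary. The finding is limited to what these documents specify.
- *An effect of 0.86 SD is hopeless against a detectable 1.87 SD.* The 0.86 is the SAP's starters-only treatment effect, not a genotype figure, and if it is read as a per-visit SD the two are on different scales. Converted, 0.86/0.816 = 1.05 SDs of the change. Power at 38 players and 50% carriers is then about 35%, against the 25% that the unconverted comparison suggests.
- *The analysis is already post hoc.* The trial is complete, but the documents do not say whether genotype and outcome data have been examined together.

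**Conclusion.** The point holds for the plan as supplied. The listed model has no parameter for a difference in supplement effect between genotypes, so it cannot answer Outcome 4 for the blood markers, and the MRI half has no stated model at all. That conclusion follows from the form of the model and rests on no assumed number.

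The primary comparison of supplement with placebo is not affected. The point should be corrected, but it does not undermine the trial.

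The precision figures do rest on assumptions: two genotype groups, the carrier share, unit SD of the analysed change and, for the per-visit conversion only, a correlation of 0.5. They show that even the right model will be imprecise at 38 players. A null result would not exclude a sizeable genotype effect.

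**What to change.** Add a dated Outcome 4 section to the SAP:

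1. State the variant or variants used for each gene and their coding.
2. For each gene, add genotype × treatment × visit, with all lower-order terms, to the longitudinal model for the blood markers. Report the genotype-by-treatment estimate with its 95% confidence interval.
3. For MRI, name the marker and fit genotype × treatment on the change from baseline to end of treatment.
4. Label the analysis hypothesis-generating, and post hoc if genotype and outcome data have already been examined.
5. State the detectable interaction at 38 players for the coding chosen, in one named SD unit.

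A lead marker and a Holm adjustment across genes are optional. Estimates with intervals alone would fit the SAP's stated emphasis on magnitude and direction for previously unstudied biomarkers.

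The cost is SAP wording and a few extra model fits, with no new visits or samples. The downside is wide intervals, which should be acknowledged when the results are reported.

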#### 9.5. Outcome 5: Other Pre-Specified Outcome Measures

- 9.5.1. **Title 5:** Conduct non-targeted metabolomic analysis to potentially identify additional potential biomarkers for sub-concussion injuries.
- 9.5.2. **Time Frame 4:** 32 weeks from baseline to one month post treatment and post end of football season.
- 9.5.3. **Description 5:** (not required)

# 10. Eligibility

10.1. **Sex:** Male

10.1.1. **Gender-Based:** (not required) No

10.2. **Age Limits:** 

10.2.1. **Minimum Age:** 18

Version Date: 03/18/2020

Study Title: Study of Effect of Docosahexaenoic Acid (DHA) and Eicosapentaenoic acid (EPA) on Biomarkers

of Sub-concussion Injuries in American Football.

IRB #: 1904553365

10.2.2. Unit of Time: Years 10.2.3. Maximum Age: NA 10.2.4. Unit of Time: NA

10.3. Accepts healthy Volunteers: Yes

# 10.4. Eligibility Criteria:

#### 10.4.1. Inclusion Criteria

- University of Arizona
- National Collegiate Athletic Association (NCAA)
- Collegiate football players
- Cleared to participate in university athletics as determined by the team physician.
- >18 years.

### 10.4.2. Exclusion Criteria

- Chronic daily anti-inflammatory medication (>20 d).
- Medications for blood lipids.
- Active fish oil or omega-3 fatty acid supplementation.
- Consumption of more than two servings of fish per week.
- Injured and unable to participate in regular schedule conditioning or competitions.
- Prior diagnosis acute concussion.
- Allergic to fish or shellfish.

Version Date: 03/18/2020

## **Study Randomization**

This study is designed to replicate and extend a study done at Texas Christian University (TCU), which looked at the effects of three doses of EPA+DHA supplementation on neurofilament light chain (NFL) levels in TCU football players over the course of a complete football season including summer training camps (Oliver et al. 2016). In that study, players were randomized to one of three supplement doses or placebo by player position, as different positions experience different degrees of head trauma. However, this resulted in very small sample sizes, and they found that the main change in their primary outcome (NFL) was for starters as opposed to non-starters, and they excluded non-starters in multiple analyses. In this study, we will modify the previous study design in two ways. First, we will use only one supplementation dose (3g DHA/EPA fish oil) vs placebo (high-oleic safflower oil). Second, we will use a block randomization scheme by which players will be randomized both by whether they are a starter or non-starter, and then by position group to receive supplementation or placebo. Starters are defined as players on the 1st and 2nd depth rosters. This definition results in the potential for n=44 starters and n=44 non-starters. The eight position groups are based on the literature (Baugh et al. 2015): offensive linemen (offensive center, guard, and tackle); defensive linemen (defensive end and defensive tackle); running backs & tight ends (fullback, running back, tight ends); linebackers (middle linebacker and outside linebacker); defensive backs (cornerback and safety); special teams (punter and kicker); wide receivers; and quarterbacks. Within blocks, we will use a random number generator to randomly assign players to treatment or placebo groups. In order to blind the contents of the capsule from both investigators and players, the supplements will then be allocated and re-labelled as "A" or "B" by a project team member who is not participating in data collection during the study.

# Power, Sample size, and Confidence intervals

This study is both an independent replication of a previous omega-3 supplementation trial with college football players, as well as an exploratory, hypothesis-generating extension that will collect additional biological data including cardiometabolic biomarkers and untargeted lipidomics. For statistical power, our primary hypothesis-driven question is whether DHA+EPA supplementation will have a protective or restorative effect based on measured levels of markers of neuronal damage, such as NFL, and whether this will vary by starter/non-starter. In this study, with a samples size of n=44 starters, n=44 non-starters, and a significance level of  $\alpha$ =0.05, we have 80% power to detect an effect size of d = 0.6, where d=( $\mu_1 - \mu_2$ )/ $\sigma$ , is the difference in the group means divided by the pooled standard deviation. The TCU study looked at the differences between starters and non-starters at multiple time points and found effect sizes ranging from 0.88 to 2.07. The TCU study also found dramatic changes in NFL levels between starters on placebo, with levels more than doubling over the season, while starters on supplementation saw a more modest increase of 35% by the end of the season. If we look only at starters, and compare the supplement (n=22) and placebo groups (n=22), we are powered to see an effect size of 0.86, well below the reported differences at many time points in the TCU study. We anticipate some other biomarkers will also change over time, and we are

well-powered to detect small to moderate effects. For previously unstudied biomarkers, our focus will be on estimating the magnitude and direction of effects in order to discover which are the most informative as markers of brain injury/recovery or omega-3 supplementation.

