# 2. Study Status

- 2.1. **Record Verification Date:** Month: Year:
- 2.2. Overall Recruitment Status: Completed: The study has concluded normally; participants are no longer receiving an intervention or being examined (that is, last participant's last visit has occurred)
  - 2.2.1. Why Study Stopped: NA
- 2.3. **Study Start date:** May 29, 2019
- 2.4. **Primary Completion date:** January 28, 2020
- 2.5. **Study Completion Date:** January 28, 2020

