### 7. Study design

- 7.1. **Primary Purpose:** Prevention
- 7.2. Study Phase: NA
- 7.3. **Interventional Study Model:** Parallel
- 7.4. **Model Description:** Participants will be randomized to treatment (3 grams DHA and EPA (2:1 weight ratio)) or placebo (3 grams high-oleic safflower oil) in a 1:1 allocation ratio based on their position on the football team and roster depth (starter vs. non-starter). Participants will be recruited as a single cohort. After screening, participants will be treated with DHA and EPA or matching placebo for 25 weeks (a full course of an American football season, including summer camp training sessions). A follow-up visit is scheduled 7 weeks after the final dosing at week 32 for recovery and adverse event evaluation.
- 7.5. **Number of Arms:** Two
- 7.6. **Masking Roles:** Participant, investigator, care provider, outcomes assessor
- 7.7. **Masking Description:** Study personnel will be kept blind to treatment assignments. The treatment assignment for each participant will be available to the investigator in a sealed envelope that may be opened only in the case of a serious adverse event which the investigator feels cannot be adequately treated without knowing the identity of the study medication. Code breakers will be collected and reviewed at the end of the study. If the blinding has been broken, then the investigator will provide documentation regarding the fact and indicate the other staff that received this information.
- 7.8. **Allocation:** Randomized
- 7.9. **Enrollment Type:** Actual
- 7.10. Number of Subjects: 38

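### The SAP's only power figures (80% at d = 0.6; d = 0.86 among starters) are for 88 potential players; the completed trial enrolled 38 and power was not restated

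*SAP*

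**What the plan says.** The SAP, under Power, Sample size, and Confidence intervals, sets out its primary question (supplementation and markers of neuronal damage such as NfL, and variation by starter status). It then says that, "with a samples size of n=44 starters, n=44 non-starters" and alpha 0.05, "we have 80% power to detect an effect size of d = 0.6". It adds that a starters-only comparison of 22 on supplement with 22 on placebo is powered for 0.86. The section names no test and does not say whether alpha is one- or two-sided.

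The SAP's Study Randomization section shows where the 44 and 44 come from. They are a roster count: "This definition results in the potential for n=44 starters and n=44 non-starters".

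The protocol reports a different size. Section 5.1 describes a "placebo controlled trial, including 38 research participants". Section 7 gives "Number of Subjects: 38" and labels the enrolment as actual. Section 2.2 gives the status as "Completed: The study has concluded normally". Neither document gives power, a detectable effect or a rationale for 38, or says how many of the 38 were starters.

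**The concern.** The two documents describe trials of different size, and the only power statements belong to the larger one. The enrolled number is 38/88 = 43% of the number behind them.

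What is at stake is interpretation. A reader who meets a non-significant NfL result and turns to the SAP will find 80% power at 0.6 SD and may take the result as fair evidence against an effect of that size. The starters claim is the most exposed, because 22 vs 22 needs 44 starters and the trial had 38 players in all. The power section's closing assurance that small to moderate changes in other biomarkers can be detected has no calculation behind it at either size.

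**Working it through.** **Inputs.** From the SAP's power section: alpha 0.05; 80% power; d defined as mean difference over pooled SD; 44 and 44; 22 vs 22. From protocol section 7: 38 participants, 1:1 allocation, hence 19 vs 19 at best. Assumed: two-sided test, no dropout.

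**Formula.** For a two-sample t-test, the noncentrality is d × sqrt(n1·n2/(n1+n2)) on n1+n2−2 degrees of freedom. Power is the noncentral t probability beyond the two-sided 5% critical value.

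**Step 1: reproduce the SAP.**
- 44 vs 44: 0.6 × sqrt(22) = 2.814, critical value 1.988 (86 df), power 79.5%; detectable d at 80% power is 0.604.
- 22 vs 22: 0.86 × sqrt(11) = 2.852, critical value 2.018 (42 df), power 79.6%; detectable d is 0.865.

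Both figures are reproduced. A one-sided test does not fit (87.4% and 87.7%). The two-sided t-test is therefore a sound inference, though still an inference. The 0.6 figure is labelled by starter status, but 88 players split 1:1 by treatment also give 44 vs 44, so the arithmetic is the same under either reading.

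**Step 2: same test, 38 players.**
- 19 vs 19: 0.6 × sqrt(9.5) = 1.849, critical value 2.028 (36 df), power 43.7%; detectable d is 0.934.
- Power at 0.86 with 19 vs 19 is 73.2%. So even if all 38 were starters, the starters figure would not be reached on this test.
- If half were starters (assumed, 9 vs 10), detectable d is 1.37.

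**Step 3: the analysis actually planned.** The SAP's section on continuous outcomes specifies a longitudinal mixed model of change from baseline, which uses more information than a single comparison. Approximate it by a baseline-adjusted mean of k follow-ups with common correlation r. The SD is multiplied by sqrt((1+(k−1)r)/k − r²), on 38 − 3 = 35 df. For example, with k = 3 and r = 0.5 the factor is sqrt(2/3 − 0.25) = 0.645. The correlations are assumed; the documents give none.

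| Follow-ups averaged (19 vs 19) | Detectable d, r = 0.3 / 0.5 / 0.7 | Power at d = 0.6 |
|---|---|---|
| 1 | 0.89 / 0.81 / 0.67 | 47% / 55% / 71% |
| 2 | 0.70 / 0.66 / 0.56 | 67% / 72% / 85% |
| 3 | 0.62 / 0.60 / 0.52 | 77% / 80% / 90% |

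The averaged rows are favourable. They assume a constant effect over time and spend no degrees of freedom on position or genotype, and the third row also counts the off-treatment recovery sample. If the effect averages only 0.4 SD over three follow-ups (assumed), power is 44% / 46% / 58%. For 9 vs 10 starters (assumed) with three follow-ups, detectable d is 0.91 / 0.89 / 0.76.

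**Step 4: how many follow-ups.** Protocol section 9.1.3 says the blood markers "will be measured at baseline, mid-treatment, post treatment, and one month (recovery) after the end of treatment", which makes three post-baseline samples. Section 5.1 mentions blood draws every month. The more specific text favours three for NfL, but the count is not settled. With six averaged (assumed), the same formula gives 0.53 / 0.54 / 0.48.

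**The case against.** The strongest reply is that a planning figure is not made false by lower enrolment. The SAP is written prospectively, presents 44 and 44 as a potential, and its arithmetic is right for those sizes. All of that stands. The gap is that the record was never reconciled with the 38 reported.

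The second reply is that 0.93 does not measure the planned analysis. This also stands. A reader might infer from 0.93 and 44% that the trial is underpowered for its primary question, and the documents do not support that. They give no correlations, no effect pattern over time and no power for the mixed model. Under favourable assumptions the model could get back to about 0.6 SD with 38 players; under less favourable ones it could not. The 0.93 is only the like-for-like update of the SAP's own calculation.

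The third reply is that the study is over, so power is moot and the confidence interval tells the reader what is needed. That is largely right, and the fix relies on it. What remains is that the SAP still offers figures for 88 to anyone interpreting a null result. The interval to use is the mixed model's. The unadjusted half-width at 19 vs 19 is 2.028 × sqrt(2/19) = 0.66 SD; under the three-follow-up approximation it would be 0.44 / 0.43 / 0.37.

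**Conclusion.** The point holds as a statement that is wrong for the trial as run, and it should be fixed. It does not undermine the planned analysis. The SAP's 0.6 and 0.86 belong to 88 potential players. On the inferred two-sided t-test, the enrolled 38 give a detectable 0.93 SD and 44% power at 0.6, assuming an exact 19 vs 19 split and no dropout, which is the best case. The starters figure of 0.86 cannot apply to a trial of 38; its replacement is unknown because no starter count is given.

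Power under the planned mixed model is undetermined. A range of roughly 0.5 to 0.9 SD is compatible with assumed correlations of 0.3 to 0.7 and one to three follow-ups.

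Two related gaps in the same SAP section would exist at any sample size. The contrast behind d = 0.6 is not named. And the earlier-study effect sizes of 0.88 to 2.07 are described as starter vs non-starter, so they do not by themselves support the claim that 0.86 lies well under the differences reported for supplement vs placebo; the supplement contrast is given only in percent, without an SD.

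**What to change.** Leave the planning paragraph as it stands and add a dated SAP note, marked as written after completion, that:

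- states that 0.6 (80% power) and 0.86 refer to 88 potential players and not to the 38 enrolled;
- gives the like-for-like detectable effect for the actual arm sizes (0.93 SD if 19 vs 19), naming the test and its sidedness, and the same for the actual starters by arm, taken from the randomization list;
- gives a range for the planned mixed model under stated correlations (for example 0.3, 0.5, 0.7), the actual number of samples, and a stated effect pattern and covariate set, after reconciling protocol sections 5.1 and 9.1.3 on sampling;
- does not carry over to 38 the assurance about detecting small to moderate effects;
- says that a non-significant NfL result is read through the 95% confidence interval from the planned mixed model, and not through the SAP's power figures or an unadjusted ±0.66 SD;
- separately, names the contrast behind d = 0.6 and records that the cited 0.88 to 2.07 are starter vs non-starter effects.

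The cost is one short document and a look at the randomization list. It needs no new data and no change to the analysis model. The downside is that the like-for-like figures become less favourable, and that the mixed-model range rests on assumed correlations.

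### The SAP's detectable effects (0.6 and 0.86) are two-group figures for 88 players; no detectable treatment-by-starter effect is given, and the protocol reports 38 enrolled.

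*SAP*

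**What the plan says.** The SAP section on power, sample size and confidence intervals sets out, for the purpose of power, a hypothesis-driven question in two parts: whether supplementation affects markers of neuronal damage such as NFL, and "and whether this will vary by starter/non-starter". The SAP's list of continuous outcome measures carries the second part into the model, which has treatment and starter status as covariates "as well as a treatment x starter/non-starter interaction".

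Two detectable effects follow. The first is introduced "with a samples size of n=44 starters, n=44 non-starters" at a 5% significance level: "we have 80% power to detect an effect size of d = 0.6", where d is a difference between two group means over the pooled SD. The second is for starters only, 22 on supplement against 22 on placebo: "we are powered to see an effect size of 0.86, well below the reported differences at many time points".

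The earlier football study is cited in two ways. One is a standardized range: "The TCU study looked at the differences between starters and non-starters at multiple time points and found effect sizes ranging from 0.88 to 2.07". The other is a percentage change: NFL more than doubled in placebo starters, while "starters on supplementation saw a more modest increase of 35% by the end of the season". No SD accompanies the percentages.

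The SAP's Study Randomization section presents 44 starters and 44 non-starters as what the roster definition could yield. Protocol 5.1 and 7.10 give 38 participants, and 7.10 sits beside an enrollment type of actual. Protocol 7.4 gives 1:1 allocation.

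**The concern.** A reader of the power section would take 0.6 or 0.86 as the trial's sensitivity for the whole primary question. Neither was calculated for the second part. Supplement versus placebo within starters is a subgroup effect. It does not test whether starters and non-starters respond differently, which needs the difference between two treatment differences and is estimated less precisely.

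Two further matters compound this. The stated sensitivity belongs to 88 players, not to the 38 reported. And the reassurance offered for 0.86 sits close to a range that the SAP describes as a different contrast. What is at stake is interpretation: a non-significant interaction from this trial could be taken to mean that starters and non-starters respond alike, when the data could not show that.

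**Working it through.** **Inputs.** From the SAP: alpha 0.05, 80% power (stated for 0.6, assumed for 0.86), d in SD units, 44 starters and 44 non-starters. From Protocol 7.4: 1:1 allocation, hence 22 per treatment-by-starter cell. From Protocol 7.10: 38 participants. Assumed: a two-sided test, because one-sided tests give about 87-89% power and do not reproduce the SAP; equal cells; equal SDs; no dropout. Power is from the noncentral t distribution.

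**Step 1, the SAP's own figures.** For two groups of n, SE = √(2/n).
- 44 vs 44: SE = √(2/44) = 0.213. Detectable effect 0.604; power at 0.6 is 79.5%.
- 22 vs 22: SE = √(2/22) = 0.302. Detectable effect 0.865; power at 0.86 is 79.6%.

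Both figures reproduce as plain two-group comparisons.

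**Step 2, the interaction on the same inputs.** With n per cell, each within-stratum treatment difference has variance 2/n. The difference between the two has variance 4/n, so SE = √(4/22) = 0.426. The pooled supplement effect has SE = √(4/88) = 0.213, exactly half. By normal approximation the detectable interaction is (1.960 + 0.842) × 0.426 = 1.19 SD; by noncentral t with 84 df it is 1.21 SD. Power is 28% for an interaction of 0.6 SD and 51% for 0.86 SD.

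**Step 3, allowing for the planned model.** The SAP says "we will use a longitudinal mixed-effects model framework to look at both individual and group-level changes from baseline over time" but gives no correlation. Take m averaged post-baseline visits, baseline adjustment, an equal correlation r between visits and a constant effect. The residual variance is then s² = (1 + (m − 1)r)/m − r², and both SEs are multiplied by s. I assume r from 0.5 to 0.8. Protocol 9.1.3 lists three post-baseline time points, so m = 3 is one reading. For r = 0.5, s² = 2/3 − 0.25 = 0.417; for r = 0.8, s² = 2.6/3 − 0.64 = 0.227.

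| 22 per cell | Pooled supplement effect (SD) | Interaction (SD) | Power, interaction 0.6 | Power, interaction 0.86 |
|---|---|---|---|---|
| One value, unadjusted | 0.60 | 1.21 | 28% | 51% |
| One value, baseline-adjusted, r 0.5-0.8 | 0.52-0.36 | 1.05-0.73 | 36-64% | 63-91% |
| Three visits averaged, r 0.5-0.8 | 0.39-0.29 | 0.78-0.58 | 58-83% | 87-99% |

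The first two numeric columns give the detectable effect at 80% power. The ratio between them is two in every row, because s cancels.

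**Step 4, at 38 players.** Equal cells would average 38/4 = 9.5.
- Pooled, 19 vs 19, unadjusted: detectable effect 0.93 SD; power at 0.6 is 44%.
- Starters only, 9.5 per arm, unadjusted: 1.36 SD; power at 0.86 is 42%.
- Interaction, unadjusted: SE = √(4/9.5) = 0.649; detectable 1.87 SD; 95% CI half-width 1.32 SD.
- Interaction, one baseline-adjusted value, r 0.5-0.8: 1.62-1.12 SD; half-width 1.14-0.79 SD.
- Interaction, three visits averaged, r 0.5-0.8: 1.21-0.89 SD; half-width 0.85-0.63 SD.

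The documents do not give the starter split. With 14 starters per arm the starters-only figure would be 1.10 SD (59% power at 0.86); with 5 per arm, 2.02 SD (22%). Unequal starter and non-starter numbers make the interaction figures larger.

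**Step 5, the benchmark.** The contrast behind 0.86 is supplement versus placebo within starters. The contrast given for 0.88-2.07 is starters versus non-starters. The percentage changes do concern treatment but, without an SD, yield no d.

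**The case against.** The best defence has four parts.

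**The arithmetic is right.** It is. A reader might infer that 0.6 and 0.86 are miscalculated; Step 1 shows that they are not.

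**The planned model is more precise than a single comparison.** This stands in part. With three averaged visits the detectable interaction at 88 players falls to 0.78-0.58 SD, so it would be wrong to infer that the planned design could not detect an interaction of 0.6 or 0.86 SD. But the SAP states no such assumptions, and any gain lowers the pooled figure equally, so one number still cannot serve both parts. The three-visit case is also idealized. The third time point falls seven weeks after the last dose (Protocol 7.4), which strains a constant effect; Protocol 5.1 mentions monthly draws; and the age, position and genotype covariates are left out.

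**A larger interaction may be the realistic one.** The SAP says the earlier study's main NFL change was in starters. If the effect D occurs only in starters, the interaction is D and the pooled effect D/2, so the two tests have the same power: at D = 1.21 SD, 80% each with 22 per cell, unadjusted. This is correct, but the SAP does not make that argument, and 0.6 would then correspond to an effect of 1.2 SD in starters.

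**The text is less definite than a critic might make it.** This stands. A reader might infer that 0.6 compares starters with non-starters; the sentence gives 44 and 44 as the sample and does not name the compared groups, and 88 players at 1:1 also give 44 per arm. A reader might likewise infer that the SAP rests 0.86 on 0.88-2.07. It does not expressly do so: the sentence just before 0.86 concerns treated and placebo starters, and the differences meant may be ones that it does not quote. Finally, 38 is an enrolment outcome and not an error in a prospective calculation.

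**Conclusion.** The point holds as a gap in what the power statement covers. The interaction is part of the question for which the SAP claims power, it is in the model, and no detectable effect is stated for it. On the SAP's own inputs that effect is about 1.21 SD against 0.60 SD for the pooled supplement effect. The twofold ratio depends on equal cells and a common variance; the absolute values depend on the visit and correlation assumptions.

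The stated 80% power also does not carry over to the reported enrolment: at 38 it is about 44% for 0.6 pooled and, if half are starters, about 42% for 0.86 in starters, both unadjusted. Under every assumption shown, the detectable interaction at 38 is at least 0.89 SD, so a non-significant term would say little about whether starters and non-starters respond differently. The SAP does not say that it would read such a result as no difference; the caution is for reporting.

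On the benchmark, the finding is limited to this: as described, 0.88-2.07 does not support a supplement-versus-placebo figure, and the SAP leaves unclear which differences it means. Whether the description is a slip cannot be settled from the documents.

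**What to change.** - State that 0.6 is supplement versus placebo pooled over starter status (44 vs 44), or name the contrast if another was meant.
- Add the detectable treatment-by-starter interaction with its assumptions (about 1.21 SD at 22 per cell for one unadjusted value, smaller under stated repeated-measures assumptions), or label that part exploratory.
- Restate the detectable effects for the 38 enrolled, using the actual starter split in place of the equal cells assumed here.
- Report the interaction as an estimate with a 95% CI, and do not treat non-significance as evidence of equal response.
- Say which contrast the reported differences and the 0.88-2.07 range refer to. Keep the range as support for 0.86 only if it is a supplement-versus-placebo difference.

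The cost is wording and reporting only, with no new data and no change in conduct. The downside is that the stated detectable effects become less favourable.
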